Title of Study: The Live Long Walk Strong Rehabilitation Program: What Features Improve Mobility Skills?

NCT 04026503

8.8.2019

Primary Outcome: The primary outcome for all aims of this study is usual Gait Speed.^{53,54} Gait speed is recorded by stopwatch over a 4-meter walking course beginning from a standing start. The fastest of 2 trials is recorded in meters/seconds. Declining gait speed is associated with heightened risk for adverse health outcomes (hospitalization, disability, death) over 1-4 years of subsequent follow up.^{53,54} Changes in gait speed of .05 and 1.0m/s are characterized as small and large clinically meaningful differences respectively.^{24,55} For Aims 2 & 3, we will identify factors that mediate changes in gait speed. Our experience with LLWS and related clinical trials identifies that the majority of participants (> 70%) exceed a .09 m/s change after treatment.]

Timing and coordination of gait

Smoothness of walking is our primary measure of timing and coordination and is an integrated measure of motor control of walking.^{37,56} It is assessed during usual over ground walking. Linear acceleration of the body is measured along three axes (vertical, anterior-posterior and medial-lateral) using a tri-axial accelerometer attached to the skin over the lumbar spine (L3 segment). Trunk accelerations are sampled at 200 Hz and used to calculate the harmonic ratio following the methodology of Menz.^{37,56} The harmonic ratio is derived in the vertical, medial-lateral and anterior-posterior directions. Higher harmonic ratios indicate greater levels of functioning. Our prior work reports mean changes of 25-30% in smoothness of walking occur with training.¹⁸

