Live Long Walk Strong SAP

NCT 04026503

8.8.2019

Initially, we will view plots and calculate simple descriptive statistics for all continuous measures, and frequencies and percentages for all categorical variables to examine the data distributions and check for data accuracy and completeness.

Derived variables (change from the baseline to each follow-up visit as well as change between consecutive visits and time intervals between visits) will be calculated and examined.

Two sample t-test will compare mean scores in changes of gait speed (Δ GS) and LLWS target attributes (ATTR) between treatment and control groups at baseline and a t-test for paired samples will evaluate changes between follow-up visits.

Multiple regression models will assess relationships between dependent and independent variables and causal mediation models will be used for mediation analysis. Mixed effects regression models will be used to analyze repeated measures. In regression and mediation models, we will examine and adjust for potential confounding factors (by design or as covariates), including baseline scores (as appropriate), age, sex, BMI, comorbidity-score, etc.

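### The mediation analysis has no check for unmeasured mediator–outcome confounding or reverse causation; a sensitivity analysis on data already collected would show how far each mediator claim can be trusted

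*SAP*

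**What the plan says.** The Protocol, under *Primary Outcome*, states the aim: "For Aims 2 & 3, we will identify factors that mediate changes in gait speed". The outcome is the same throughout: "The primary outcome for all aims of this study is usual Gait Speed".

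The method is one clause in the SAP's fourth paragraph: "causal mediation models will be used for mediation analysis". That paragraph adds adjustment of the regression and mediation models for potential confounders, through design or as covariates. It names baseline scores, age, sex, BMI and a comorbidity score, and leaves the list open. The Protocol section *Covariates & potential confounding variables* records more: depression, pain, falls and illnesses, balance confidence, cognition, range of motion and, every 4 weeks, physical activity and exercise engagement.

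On timing, the SAP's second paragraph derives "change from the baseline to each follow-up visit as well as change between consecutive visits and time intervals between visits". No sentence links any of these intervals to the mediation model. No sensitivity analysis for unmeasured confounding is named.

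For smoothness, the primary measure of timing and coordination, the Protocol says: "It is assessed during usual over ground walking".

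**The concern.** Randomisation (assumed; the supplied text mentions treatment and control groups but not allocation) protects two effects: treatment on the attribute and treatment on gait speed. It does not protect the path from attribute to gait speed, because nobody is assigned a level of smoothness or leg power. A causal reading of that path needs two conditions: no unmeasured common cause, and an attribute that acts on gait speed rather than the reverse.

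Both can fail. General recovery or effort on the test day could raise an attribute and gait speed together. Reverse influence is most plausible for smoothness, which is also taken during usual walking. In either case the fitted model shows an indirect effect that is not there. The question in the study title, which features of the programme improve mobility skills, could then be answered with the wrong features.

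**Working it through.** **Nothing to reproduce.** The documents state no N, SD, treatment effect, mediation effect or residual correlation. The figures below show how the method behaves under assumed inputs.

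**Assumptions.** 1:1 allocation; N=100 or 200; treatment effect of 0.5 SD on the attribute (a) and on gait speed; true attribute effect on gait speed of zero; correlation ρ between the two residuals. A mediator is declared when both paths have two-sided p<0.05.

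**Step 1, treatment to attribute.** The standard error is 2/√N: 0.200 at N=100 and 0.141 at N=200. The ratios 0.5/SE are 2.50 and 3.54, giving power of 0.697 and 0.940 (noncentral t).

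**Step 2, attribute to gait speed.** With a true effect of zero, the coefficient of the attribute, given treatment, tends to ρ. Its ratio to its standard error is ρ√(N−3)/√(1−ρ²). For N=100 and ρ=0.3 this is 0.3×9.85/0.954 = 3.10, with power 0.866.

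**Step 3, both significant.** Multiply the two powers. The last column for each N is from simulation (at least 2,000 trials per setting).

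| ρ | N=100: ratio, power | product | simulated | N=200: ratio, power | product | simulated |
|---|---|---|---|---|---|---|
| 0 | 0, 0.050 | 0.035 | 3.5% | 0, 0.050 | 0.047 | 4.6% |
| 0.1 | 0.99, 0.165 | 0.115 | 13% | 1.41, 0.289 | 0.272 | 27% |
| 0.2 | 2.01, 0.512 | 0.357 | 36% | 2.87, 0.814 | 0.765 | 76% |
| 0.3 | 3.10, 0.866 | 0.603 | 61% | 4.41, 0.993 | 0.933 | 93% |
| 0.4 | 4.30, 0.989 | 0.689 | 67% | 6.13, 1.000 | 0.940 | 94% |

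At ρ=0 the false rate stays at or below 5%, so the test is sound when its assumption holds.

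**Step 4, size of the false effect.** It is a×ρ: 0.05, 0.10, 0.15 and 0.20 SD for ρ=0.1 to 0.4. Divided by a total effect of 0.5 SD, the apparent proportion mediated is 10% to 40%. This merely restates ρ, because both treatment effects were set to 0.5.

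**Step 5, reverse causation alone.** Let gait speed drive the attribute with coefficient k, with treatment reaching the attribute only through gait speed. The false indirect effect is 0.5k×k: 0.045 SD at k=0.3 and 0.125 SD at k=0.5, or 9% and 25% of the total effect. In simulation a mediator is declared in about 9% and 23% of trials at N=100, and 19% and 42% at N=200.

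**Step 6, does a lag help?** Set the attribute at one visit against gait speed at the next, with values taken as baseline-adjusted and an assumed between-visit gait-speed correlation of 0.6 to 0.8. At k=0.5 the false rate is 23–24% same-visit and 20–23% lagged at N=100; at N=200 it is about 42% for both. At k=0.3 the lag helps only partly (from 9–10% to 4–8% at N=100). The false path survives because gait speed persists between visits. Adding gait speed at the mediator visit to the model cuts the rate to about 1–3%.

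**Step 7, does the sensitivity analysis work?** In a linear model without interaction, the indirect effect reaches zero when the assumed ρ equals the observed residual correlation of attribute and gait speed. Testing against the true ρ instead of zero returned the false rate to about 3–6% in every setting (N=100 to 200, a=0.5 to 0.8 SD, ρ=0 to 0.5). In practice ρ is unknown, so the useful output is the value at which the effect vanishes.

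**The case against.** The strongest reply is that the plan controls confounding more fully than the four background variables suggest. The SAP includes baseline scores and leaves its list open, and the Protocol measures many further covariates. Exercise engagement partly captures adherence, and the illness calendars bear on recovery. This stands and narrows the point to unmeasured common causes and to reverse direction, which covariates of this kind do not remove. One caution remains: activity and engagement are recorded after baseline, and if treatment changes them, ordinary covariate adjustment does not handle them cleanly.

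The second reply is that every magnitude above is assumed. That also stands. Nothing in the documents shows a residual correlation of 0.2 to 0.4 after adjustment, and at 0.1 the false rate is much lower.

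Third, smoothness and gait speed are different measurements: an accelerometer harmonic ratio, and a stopwatch time over 4 metres. The documents give no relation between them, so reverse influence is plausible but not shown.

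Fourth, the supplied text looks like an excerpt: the Protocol refers to a section 3.G.vi that is not included, and no visit schedule appears. Time order could be set elsewhere. The point is limited to what was supplied.

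A reader might infer that the SAP plans to correlate same-visit changes. It does not say so; it leaves the pairing open. A reader might also infer that lagging the mediator would settle the matter. Step 6 shows that a lag adjusted only for baseline does not remove reverse causation, and no lag removes a persistent common cause.

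**Conclusion.** The point holds as a cheap improvement. The plan seeks causal mediators, relies on adjustment for measured confounders, and commits to no check of the assumption on which the causal reading depends. Under the stated assumptions (0.5 SD effects, no true mediator effect), a modest residual correlation is enough to make a false mediator likely. These rates illustrate sensitivity and are not predictions for this trial.

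The documents do not support two stronger conclusions that a reader might draw. They do not show that the attributes will be wrongly named as mediators, since the residual correlation is unknown. Nor do they put the between-group comparison of gait speed in doubt, because that comparison does not use the mediator path.

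**What to change.** Add to the SAP:

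1. **Sensitivity analysis for every attribute.** Report the residual correlation at which the indirect effect reaches zero, and the indirect effect at correlations of 0.1, 0.2, 0.3 and 0.4. Call an attribute a causal mediator only with that result beside it; otherwise label the finding associational.
2. **A supporting lagged model**, if attributes are measured at two or more follow-up visits. Set the attribute at the earlier visit against gait speed at the next, adjusted for baseline attribute, baseline gait speed and gait speed at the mediator visit. Report the same-visit model beside it.
3. **Smoothness.** Make no causal mediator claim from the same-visit model alone, or from a lagged model adjusted only for baseline.

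The cost is SAP wording and extra analysis of data already collected. The lagged model has a real drawback: adjusting for gait speed at the mediator visit removes any effect already expressed by then, and conditions on a variable that treatment affects. That is why it is supporting only. It should not be presented as a cure for unmeasured common causes; item 1 addresses those.
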